3. OVERALL STUDY INFORMATION

The following information will be analyzed descriptively and corresponding details on the subject level will be provided in data listings:

- Subject overview
- Inclusion/exclusion criteria (will be listed only)
- Protocol deviations
- Attended visits with dates
- Study completion
- Study drug administration

4. BASELINE EVALUATION

The following information will be analyzed descriptively and corresponding details on the subject level will be provided in data listings:

- Demographic information
- Medical and ophthalmic histories
- Prior/concomitant medication
- Non-pharmacologic treatments and procedures

5. PHARMACOKINETICS / PHARMACODYNAMICS ANALYSIS

Pharmacokinetics:

The PP-001 concentrations in plasma will be listed.

Pharmacodynamics:

The following information will be analyzed descriptively and corresponding details on the subject level will be provided in data listings (Note: Some parameters are just available for either Cohort 1-3 or Cohort 4):

- Best corrected visual acuity
- Visual field
- Intraocular pressure
- Dilated fundoscopy
- Fundus photography
- Amsler grid
- Ocular Surface Disease Index
- Tear film osmolarity
- Slit lamp examination
- Tear film break up time
- Corneal staining with fluorescein

- Conjunctival staining using lissamine green
- Evaluation of ocular discomfort

6. SAFETY ANALYSIS

6.1 Adverse Events

The following information will be analyzed descriptively and corresponding details on the subject level will be provided in data listings:

- Adverse Event (AE)
- AEs leading to premature discontinuation from the study drug
- Serious AEs
- AEs by severity
- AEs by causality
- AEs by SOC and PT

Definitions:

- In tables showing subjects with AEs by maximum severity, subjects will be counted only in the highest grading category, but events will be counted in each reported grading category.
- In tables showing AEs by maximum causality, subjects will be counted only in the strongest relationship category, but events will be counted in each category.

6.2 Laboratory Parameters

The following information will be analyzed descriptively and corresponding details on the subject level will be provided in data listings:

- Laboratory results

Laboratory results for the different laboratory parameters will be shown by time point.

6.3 Other Safety Parameters

The following information will be provided in data listings:

- Vital signs
- Physical examination
- Electrocardiogram
- Pregnancy Test

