9.4 Criteria for Evaluation

9.4.1 Safety Analysis Variables

Safety parameters (i.e., changes in clinical signs and symptoms from physical exam, changes in clinical laboratory parameters, vital signs and AEs).

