9.6 Safety Analysis

Safety will be evaluated in the Safety Analysis Set by presenting summaries of AEs and vital signs.

Summary tables will be provided for all treatment-emergent AEs (TEAEs). A TEAE is defined as an AE with a start date and time on or after the first dose of study drug. Adverse events will be coded using the Medical Dictionary for Regulatory Activities (MedDRA®). The number and percentage of subjects with TEAEs will be tabulated by system organ class and MedDRA Preferred Term for each treatment group and by severity and relationship to treatment.

Adverse events leading to premature discontinuation from the study drug and serious TEAEs will be presented either in a table or a listing.

Descriptive statistics of vital signs and the change from baseline for each scheduled evaluation will be summarised at each study visit and the worst overall post-baseline value will be provided. The number and percent of subjects with treatment-emergent values with potential clinical significance will be tabulated.

Descriptive statistics of laboratory parameters and the change from baseline for each scheduled evaluation will be summarised at each study visit. The number and percent of subjects with treatment-emergent values of potential clinical significance will be tabulated by parameter.

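### The SAP reduces vital signs, a primary endpoint component, to a listing and names no laboratory count of potentially clinically significant values. Protocol 9.6 requires both, and SAP 2.11 does not declare the change.

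*SAP*

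**What the plan says.** Protocol 9.6 opens with "Safety will be evaluated in the Safety Analysis Set by presenting summaries of AEs and vital signs".

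For vital signs it then requires three things:
- Statistics and change over time: "Descriptive statistics of vital signs and the change from baseline for each scheduled evaluation will be summarised at each study visit".
- One extreme reading per subject, in the sense that "the worst overall post-baseline value will be provided".
- PCS counts, worded as follows: "The number and percent of subjects with treatment-emergent values with potential clinical significance will be tabulated".

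The synopsis repeats the promise to summarise PCS vital signs.

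For laboratory parameters protocol 9.6 requires two things:
- Statistics and change over time, in near-identical wording: "Descriptive statistics of laboratory parameters and the change from baseline for each scheduled evaluation will be summarised at each study visit".
- PCS counts again, this time split by test: "The number and percent of subjects with treatment-emergent values of potential clinical significance will be tabulated by parameter".

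Protocol 9.4.1 words the safety variables as "changes in clinical laboratory parameters, vital signs and AEs". SAP 1.3.1 keeps laboratory tests and vital signs as components of the primary endpoint.

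The SAP's outputs are narrower. Sections 6.1 (adverse events) and 6.2 (laboratory) promise descriptive analysis plus listings. Section 6.3, which covers vital signs, says only "The following information will be provided in data listings". In SAP 7.1 the one laboratory table is Table 4.7, results by time point; there is no vital-sign table and no PCS table. In SAP 7.2 vital signs appear as Listing 4.4. SAP 2.11, the section for changes to the planned analysis, removes concomitant medication from the primary endpoint and reports the early stop of Cohort 3 and the addition of Cohort 4. It does not mention vital signs or laboratory PCS counts.

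**The concern.** A team that follows the SAP exactly will not produce summaries that the protocol requires for two components of the primary endpoint. The primary objective is safety and tolerability of ascending doses compared with placebo, and a listing gives no summary on which to make that comparison. Readers would have to work through individual values and derive changes themselves, against a baseline that neither document defines.

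A sponsor may narrow a planned analysis, but the SAP has a section for declaring that. It was used for concomitant medication and not for this.

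**Working it through.** The documents give no power or sample-size calculation, so there is no figure to reproduce. The check is a comparison of outputs, followed by a count that shows scale.

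**Outputs side by side** (each required statistic counted separately; another partition would give another total)

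| Protocol 9.6 output | In the SAP? |
|---|---|
| Vital signs: statistics by visit | No, Listing 4.4 only |
| Vital signs: change from baseline | No |
| Vital signs: worst post-baseline value | No |
| Vital signs: n (%) PCS | No |
| Laboratory: statistics by visit | Yes, Table 4.7 |
| Laboratory: change from baseline | Not named |
| Laboratory: n (%) PCS by parameter | No |

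Vital signs 4 + laboratory 3 = 7. The SAP names 1, omits 4 + 1 = 5, and leaves 1 unnamed. SAP 6.3 also gives physical examination, ECG and pregnancy test a listing only, but protocol 9.6 sets no summary for these, so they are not part of this point.

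**Post-dose vital-sign records at planned size, full attendance**

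Inputs:
- Protocol Table 1 (cohorts 1-3): Days 2, 6, 8, 9, 10, 15, 19 and 21 = 8 visits.
- Protocol Table 2 (cohort 4): Days 1, 2, 7, 11 and 13 = 5 visits, or 6 if the Day 0 reading follows the dose, which the table does not state.
- Planned subjects: cohorts 1-3, 18 PP-001 and 6 placebo; cohort 4, 14 PP-001 and 7 placebo.

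Records = subjects × visits:
- PP-001: 18 × 8 + 14 × 5 = 214; with 6 visits, 18 × 8 + 14 × 6 = 228.
- Placebo: 6 × 8 + 7 × 5 = 83; with 6 visits, 6 × 8 + 7 × 6 = 90.
- Total: 214 + 83 = 297 to 228 + 90 = 318.
- Cohort 3's planned share: 8 × 8 = 64.

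**Laboratory pairs at planned size**

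The full panel is taken at screening and on Day 21 (cohorts 1-3) or Day 13 (cohort 4); Day 0 in cohort 4 is the alcohol and drug screen only. Pairs: PP-001 18 + 14 = 32, placebo 6 + 7 = 13, total 45. With complete pairs the mean change equals the difference between the two means in Table 4.7, although its standard deviation cannot be recovered that way. The firm laboratory loss is therefore the PCS counts.

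**What the PCS counts need**

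Protocol Appendix 2 lists values of potential concern, but protocol 9.6 does not say that these are the PCS limits. Its blood-pressure limits are changes from baseline, so they cannot be applied until baseline is defined. Its heart-rate limits are for supine and erect posture, while protocol 6.1.2 measures heart rate sitting.

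**The case against.** **The SAP governs the detail and is flexible.** SAP 2.1 describes itself as general guidelines, but also as a fuller account of the protocol's analysis. Protocol section 9 allows additional analyses, not removals. The notes in SAP 7 deal with numbering, labels and splitting of outputs. None of this restores an output that the SAP leaves out.

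**Nothing is lost.** This largely stands. Every value is listed with treatment group shown (SAP 2.10), the tables can be programmed later from the same data, and the p-values are exploratory. What does not carry over is prespecification: SAP 2.3 unblinds the statistical team after database closure, so a baseline or a heart-rate limit chosen after that would be chosen with treatment known.

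**Adverse events capture what matters.** This stands in part. Protocol section 7 excludes laboratory abnormalities from adverse events unless they come with signs and symptoms or need medical intervention, and the SAP plans no table of the investigator's clinical-significance marks. A reader might extend that exclusion to vital signs, but the text concerns laboratory findings only. Vital-sign events can appear in the adverse event tables, although those are not the summaries that protocol 9.6 requires.

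**The protocol does not promise these tables by group.** This is correct as a reading of section 9.6, where the reference to each treatment group is attached to treatment-emergent adverse events. Presentation by group is an inference from the general table columns in SAP 2.4 and from the comparison with placebo in the primary objective. It is a sound inference, but not an express promise.

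**Conclusion.** The point holds and should be fixed. Vital signs lose all four summaries required by protocol 9.6, laboratory data lose the PCS counts, laboratory change from baseline is left unnamed, and SAP 2.11 declares none of this. The consequence is incomplete and recoverable reporting of primary safety data, with no effect on any error rate.

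Three stronger readings are tempting, and the documents do not support them:
- That 297 to 318 records and 45 laboratory pairs are maxima. They assume planned size and full attendance. Cohort 3 stopped early, which lowers the count by an amount the documents do not give. Protocol 6.8 replaces subjects who withdraw before day 21 for reasons other than adverse events, which can add records.
- That vital signs would never be reviewed by group. Protocol 10.2 names ophthalmic examinations and adverse events as what is monitored, but leaves details to a DSMB charter that is not among the documents.
- That safety signals would go unreported. The listings and the adverse event tables remain.

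The conclusion itself rests on the text of the two documents and not on the record counts.

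**What to change.** Before database closure:

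1. Add to SAP 6.3 and 7.1 the vital-sign tables: statistics by visit, change from baseline, worst post-baseline value and n (%) PCS. Add to SAP 6.2 and 7.1 the laboratory change from baseline and n (%) PCS by parameter. Use the treatment columns of SAP 2.4.
2. State the baseline for each table. For laboratory tests, screening is the only full pre-dose panel. For vital signs in cohort 4, say whether the Day 0 reading precedes the dose.
3. Confirm whether protocol Appendix 2 supplies the PCS limits, and reconcile its supine and erect heart-rate limits with the sitting measurement in protocol 6.1.2. This must come before the heart-rate count is programmed.
4. Declare and justify in SAP 2.11 any protocol 9.6 summary still omitted.

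The cost is a few tables from data already collected, one baseline statement, one clarification of limits and, if needed, one entry in SAP 2.11. Items 2 and 3 need decisions before programming, so the order matters.

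As a separate and lesser item, SAP 5 plans only a listing of plasma concentrations, while protocol 9.7 also requires a graph and a summary by time point, day and treatment group. Restore these or declare the change.

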7. LIST OF TABLES AND DATA LISTINGS

Some additional notes:

- Every table number has as prefix 14.
- Every listing number has as prefix 16.2.
- In some cases numbering and labels may be adjusted in the analysis. Here are some examples:
 - Laboratory result table may be subdivided into several tables for the different laboratory parameters
 - Tables are split up by cohort, e.g. show table only for Cohort 1-3 and repeat it for Cohort 4
 - Listings do not fit on one page in the output and have to split up into several parts.

7.1 List of Tables

No.	Legend	Comment
Overall study information		
1.1.1	Subject overview (all subjects)	
1.1.2	Protocol deviations (safety analysis set)	
1.1.3	Attended visits with dates (safety analysis set)	
1.1.4	Study completion (safety analysis set)	
1.1.5	Study drug administration (safety analysis set)	
1.2.2 -	Repeat tables for ITT analysis set, if not the same as safety analysis set.	
1.2.5		
Baseline evaluation		
2.1.1	Summary table of demographic information (safety analysis set)	
2.1.2	Summary table for medical and ophthalmic histories and prior and concomitant medication (safety analysis set)	
2.1.3	Non-pharmacologic treatments and procedures (safety analysis set)	
2.2.1 -	Repeat tables for ITT analysis set, if not the same as safety analysis set.	
2.2.3		
Pharmacodynamics Analysis		
3.1.1	Pharmacodynamics by time point (ITT analysis set)	
3.2.1	Repeat table for PP analysis set.	
Safety Analysis		
4.1	Summary table for adverse events (safety analysis set)	Including tests described in section 2.5.
4.2	Adverse events by SOC and PT (safety analysis set)	
4.3	Adverse events by severity (safety analysis set)	
4.4	Adverse events by maximum severity (safety analysis set)	"By maximum severity" is explained in section 6.1.
4.5	Adverse events by causality (safety analysis set)	
4.6	Adverse events by maximum causality (safety analysis set)	"By maximum causality" is explained in section 6.1.
4.7	Laboratory results by time point (safety analysis set)	

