Sample Size for cohorts 1-3: Twenty-four (24) healthy female or male subjects will be enrolled in the study. No power calculations have been performed and the sample size is based on the requirements of the study design.

Sample Size for cohort 4: Twenty-one (21) subjects with diagnosed ocular surface inflammation will be treated. No power calculations have been performed and the sample size is based on the requirements of the study design.

Treatment Comparison of Interest: a comparison will be made between the cohorts with regard to safety and tolerability.

Analysis Populations

- *Intent-to-treat (ITT) Analysis Set:* all subjects regardless of whether or not the subject received study drug
- *Per-protocol Analysis Set:* all ITT Analysis Set subjects who have no major protocol deviations and who complete the study up to the end of the post-study assessments
- *Safety Analysis Set:* all subjects who receive any amount of study drug. All safety analyses will be conducted in this population
- *Pharmacokinetic Analysis Set:* all subjects who receive any amount of study drug will be included in the formal analysis of pharmacokinetic parameters providing they have at least one evaluable pharmacokinetic sample

Variables for Analysis:

Primary

- Safety parameters (i.e., changes in clinical signs and symptoms from physical exam, changes in clinical laboratory parameters, vital signs and adverse events [AEs])

Secondary

- Plasma concentrations of PP-001 and associated derived parameters (cohorts 1-3 only)

Safety analysis

The incidence of treatment-emergent AEs, serious AEs (SAEs), deaths and discontinuations of study drug due to an AE or SAE will be summarised by System Organ Class and Preferred Term according to the Medical Dictionary for Regulatory Activities, by relationship to study drug, and by severity. The incidence of potentially clinically significant vital signs will be summarised.

Pharmacokinetic analysis

The concentration of PP-001 in plasma will be measured in blood samples taken at Day 0 pre and post dose (0.5 h and 1h \pm 5 minutes after dosing) and on Day 8 and 19 at 0.5 h \pm 5 minutes after last instillation. Samples will be shipped to A&M GmbH, [name] for analysis. Only subjects of cohorts 1-3 will participate in pharmacokinetic sampling.

Table 1. Schedule of Assessments and Procedures (Cohorts 1-3):

Phase	Screening	Part I				Part II							Follow up

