7. ADVERSE EVENTS

An AE is any untoward medical occurrence in a patient or clinical investigation subject administered a pharmaceutical product that does not necessarily have a causal relationship with this treatment. An AE can therefore be any unfavourable and unintended sign (including an abnormal laboratory finding), symptom, or disease temporally associated with the use of an IP, whether or not related to the IP.

Any pre-existing conditions or signs and/or symptoms present in a subject before the start of the study (i.e., before informed consent) should be recorded as medical/surgical history. Any medical occurrences that are new or worsened from the time of informed consent and up to and including the final visit must be reported as AEs or SAEs. All AEs and SAEs must be recorded irrespective of whether they are considered drug-related.

Subjects will be monitored throughout the study for adverse reactions to the study medications and/or procedures at each study visit. Questions will be posed in a non-leading manner so as not to bias the response. In addition to questioning at specific time points, subjects will be encouraged to report any AEs spontaneously. Subjects will also record any AEs occurring during the outpatient phase in a subject diary card. Any subject with an AE, SAE or clinically significant abnormal laboratory test value will be evaluated by the Investigator, or a monitoring physician, and will be treated and/or followed up until the symptoms or values have resolved or are assessed as stable by the Investigator. A physician, either at the Investigative site or at a nearby hospital emergency room, will administer treatment for any SAEs. Where appropriate, medical tests and examinations may be performed to ensure that an AE has fully resolved.

Adverse events and SAEs will be monitored throughout the study from the time a subject provides consent through to the final follow-up visit. Whenever possible, a specific disease or syndrome rather than individual associated signs and symptoms should be identified by the Investigator and

recorded on the subject's eCRF. However, if an observed or reported sign or symptom is not considered a component of a specific disease or syndrome by the Investigator, it should be recorded as a separate AE on the subject's eCRF.

Each AE or SAE reported will be assessed for severity and the date and time of onset (if available), relationship to dosing, duration and outcome of each event will be noted.

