7.3 Serious Adverse Events

An SAE is any untoward medical occurrence that:

- Results in death
- Is life-threatening
- Results in persistent or significant disability/incapacity
- Requires in subject hospitalisation or prolongation of existing hospitalisation
- Is a congenital anomaly/birth defect
- Is an important medical event

NOTE: medical or scientific judgment should be exercised in deciding whether reporting is appropriate in other situations, such as important medical events that may not be immediately life threatening or result in death or hospitalisation but may jeopardise the subject or may require medical or surgical intervention to prevent one of the other outcomes listed in the above definition. These should also be considered serious. Examples of such events are invasive or malignant cancers, intensive treatment in an emergency room or at home for allergic bronchospasm, blood dyscrasias or convulsions that do not result in hospitalisation or development of drug dependency or drug abuse.

All SAEs for subjects occurring from the time of informed consent through to the follow-up visit must be reported to Panoptes Pharma GesmbH or their representative within 24 h of the knowledge of the occurrence (this refers to any AE that meets one or more of the aforementioned serious criteria).

The SAE form should be completed in as much detail as possible but a lack of complete information should not delay the reporting of the SAE.

There may be situations when an SAE has occurred and the Investigator has minimal information to include in the initial report to the Clinical Trials Coordination Centre, Medical University of Vienna. However, it is very important that the Investigator always makes an assessment of causality for every event prior to transmission of the SAE report form to Clinical Trials Coordination Centre, Medical University of Vienna. The Investigator may change his/her opinion of causality in light of follow-up information, amending the SAE report form accordingly. The causality assessment is one of the criteria used when determining regulatory reporting requirements.

The Investigator will provide the assessment of causality as per instructions on the SAE

If an SAE occurs during this study, the following (Sponsor) personnel should be contacted:

Clinical Trials Coordination Centre, Medical University of Vienna:
[contact]

Panoptes Pharma:

[name]:

Phone (office and after-hours): [name]

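### The SAP's adverse event tables and Fisher tests have no treatment-emergent window, so a dosed subject's pre-dose event can count in an arm's incidence, contrary to protocol 9.6

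*SAP*

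**What the plan says.** **Protocol, analysis.** Section 9.6 states: "Summary tables will be provided for all treatment-emergent AEs (TEAEs"). It then gives the definition: "A TEAE is defined as an AE with a start date and time on or after the first dose of study drug". The same section applies the restriction to the tables by system organ class and preferred term, by severity and by relationship. The synopsis is in line: "The incidence of treatment-emergent AEs, serious AEs (SAEs), deaths and discontinuations of study drug due to an AE or SAE will be summarised".

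**Protocol, collection.** Recording starts earlier than that. Section 7 states: "Adverse events and SAEs will be monitored throughout the study from the time a subject provides consent through to the final follow-up visit". What must be reported there is described as "Any medical occurrences that are new or worsened from the time of informed consent and up to and including the final visit". Section 7.3 sets the same start for serious events: "All SAEs for subjects occurring from the time of informed consent through to the follow-up visit must be reported". Screening is scheduled for Day -14 to Day -2 and first dosing for Day 0, so there is a real interval in which a pre-dose AE can be recorded.

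**SAP.** Section 6.1 lists AEs, serious AEs, AEs leading to discontinuation, and breakdowns by severity, causality and coded term, with no onset window. In section 7.1, Table 4.1 is titled "Summary table for adverse events (safety analysis set") and carries the Fisher tests of section 2.5; Tables 4.2 to 4.6 are labelled in the same unrestricted way. Neither the term treatment-emergent nor its abbreviation appears in the SAP. Section 2.9.3 defines the safety set by receipt of any study drug, placebo included. Section 2.11 declares one change of endpoint (concomitant medication) and nothing about the AE window.

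**The concern.** The SAP describes itself in 2.1 as a fuller account of the protocol's analysis, yet on this point it drops a restriction that the protocol states outright. A programmer working from SAP 6.1 and 7.1 would tabulate every AE recorded in a dosed subject, including one that followed a screening procedure and preceded any exposure.

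AEs are the first listed component of the primary endpoint, and in a small phase I study the incidence by arm is the main AE output. Two distortions are possible:

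- A subject whose only AE is pre-dose raises that arm's incidence.
- In Table 4.4, which counts each subject at the highest grade, a pre-dose event of higher grade would set that subject's grade. Events are still counted in every grade reported.

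**Working it through.** There is no figure in the plan to reproduce: neither document gives a power calculation or an expected AE rate. The check is a comparison of texts, followed by illustrations on the planned arm sizes.

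**1. Does anything in the SAP restore the window?**

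| Item | Protocol | SAP |
|---|---|---|
| Events summarised | Onset at or after first dose (9.6) | Adverse events, no window (6.1; Tables 4.1 to 4.6) |
| Events recorded | From consent (7, 7.3) | Not restricted |
| Population | Subjects given any study drug (9.3.3) | Same, including placebo (2.9.3) |
| Declared change | – | None on this point (2.11) |

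The population filter acts on subjects. A dosed subject's screening AE passes through it.

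**2. Effect of one subject.** Planned columns are 6 (each PP-001 arm of Cohorts 1 to 3, and their pooled placebo), 18 (Cohorts 1 to 3 PP-001 pooled), 14 (Cohort 4 PP-001) and 7 (Cohort 4 placebo). One subject whose only AE is pre-dose moves incidence by 100/n:

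- 100/6 = 16.7 points
- 100/7 = 14.3 points
- 100/14 = 7.1 points
- 100/18 = 5.6 points

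A subject who also has a treatment-emergent AE does not move overall incidence. SAP 2.11 says Cohort 3 stopped early, so its actual size and the pooled size may be smaller.

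**3. How often a column would be affected.** Assumptions, not in the documents: each subject has a pre-dose AE with probability q and a treatment-emergent AE with probability p, independently. The chance that a column holds at least one pre-dose-only subject is 1 − (1 − q(1 − p))^n.

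| p | n | q = 1% | q = 5% | q = 20% |
|---|---|---|---|---|
| 60% | 6 | 2.4% | 11.4% | 39.4% |
| 60% | 14 | 5.5% | 24.6% | 68.9% |
| 20% | 6 | 4.7% | 21.7% | 64.9% |
| 20% | 14 | 10.6% | 43.5% | 91.3% |

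Example: p = 60%, q = 5%, n = 14 gives 1 − (1 − 0.05 × 0.40)^14 = 1 − 0.98^14 = 0.246.

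**4. Exploratory p-values, Cohort 4 (14 vs 7, two-sided Fisher, assumed counts).**

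- 8/14 vs 0/7 gives p = 0.018. One pre-dose-only placebo subject makes it 8/14 vs 1/7, p = 0.159.
- 6/14 vs 0/7 gives p = 0.061. One pre-dose-only PP-001 subject makes it 7/14 vs 0/7, p = 0.047.

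These are chosen cases. Over all 217 ways of adding one subject with an AE to either arm, 26 (12%) cross 0.05.

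**5. Expected effect in the placebo comparisons.** The observed rate is 1 − (1 − p)(1 − q). With equal q in both arms, the observed risk difference is (1 − q) times the true one. For 60% vs 10%, a difference of 0.50 becomes 0.495, 0.475 or 0.40 at q = 1%, 5% or 20%. The comparisons of Cohort 1, 2 or 3 with Cohort 4 set healthy volunteers against patients and are not randomised, so equal q cannot be assumed there.

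**The case against.** The strongest reply is that the SAP is silent rather than contradictory. It presents itself as elaborating the protocol, nothing in it revokes the 9.6 definition, and section 7 allows labels to be adjusted. The protocol's own wording is also mixed: the endpoint in 2.3 and the safety variable in 9.4.1 name AEs without a window, and in the synopsis it is unclear whether the qualifier extends to serious AEs, deaths and discontinuations. This part stands as a limit on the claim. The SAP permits pre-dose events in the tables; it does not announce them. The reply still does not supply a filter, because the SAP neither restates the definition nor refers to it.

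The second reply is that the consequences are small. Most of it stands:

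- The larger probabilities in the table need q = 20%, which is high for a short interval in subjects required to be in good general health. At q = 1% they are about 2% to 11%.
- With equal treatment-emergent rates in both Cohort 4 arms (20%, 30% or 60%), the same model puts the chance of crossing 0.05 at about 0.2% to 0.4% for q = 1% and about 3% at most for q = 20%.
- SAP 2.5 calls the p-values exploratory.
- A pre-dose event would probably be rated unrelated in Tables 4.5 and 4.6, and Listing 4.1 allows the treatment-emergent counts to be rebuilt.

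None of this corrects the incidences in Tables 4.1 to 4.4.

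A third point is that the AE arrows in the visit schedules may start at Day 0. Their layout cannot be relied on in the text available, and sections 7 and 7.3 state explicitly that collection starts at consent.

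**Conclusion.** The concern holds: the SAP as written departs from the AE analysis in protocol 9.6 without declaring it, in the tables that report the first listed component of the primary endpoint. Confidence in the omission is high, because it rests on the texts alone.

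The size is modest and partly unknown. The firm figure is the shift from one pre-dose-only subject: 5.6 to 16.7 points, depending on the column, at planned sizes. How often that happens rests on assumed values of q and p and on their independence. In the two placebo comparisons the expected effect under equal q is mild dilution; in the three non-randomised comparisons with Cohort 4 the direction cannot be stated. No confirmatory conclusion depends on it. It should be fixed before analysis, but it does not threaten the study.

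**What to change.** In SAP 6.1, 2.5 and 7.1, restrict Tables 4.1 to 4.6 and the Fisher tests to treatment-emergent AEs as defined in protocol 9.6. List pre-dose AEs separately, or flag them in Listing 4.1.

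Add a classification rule for incomplete onset. The definition uses date and time, but protocol section 7 says each event "will be assessed for severity and the date and time of onset (if available"), and SAP 2.7 rules out imputation. A workable rule counts an AE on the first dosing day with missing onset time as treatment-emergent. The same paragraph should say how a missing or partial onset date is classified.

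If all-AE tables are what the sponsor wants, declare and justify that in SAP 2.11.

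The cost is a few lines of SAP text and one derived flag. AE onset and dosing dates are already collected, so no new data are needed.
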